### **3. SUBJECT IDENTIFICATION, RECRUITMENT, AND CONSENT**

#### **3.1 Method of Subject Identification and Recruitment**

Participants will be assigned de-identified code numbers to maintain confidentiality. This code will be used to label all de-identified documents and data files relating to the subject.

Selection will occur as a function of the criteria above.

#### **3.2 Process of Consent**

Consent is an on-going process that starts when you first inform potential subjects about the study and ends when the subject's study participation is completed.

**a)** Written informed consent will be obtained by standard procedures approved by the University of Rochester Medical Center Research Subjects Review Board (RSRB). Consent form will be e-mailed or sent via letter or fax to the subject (if an adult) or to the subject's parent/guardian for their review at least 24 hours before their scheduled appointment. Informed consent will be obtained in person by one of the study investigators prior to any study-related activities, typically as the first line of action when a subject comes in for the experiment they are participating in.

The consent form will be reviewed and the participant or guardian will be given as much time as they desire to decide. If they would like to take more time to seek input from other individuals before deciding about participation, this will be allowed and the visit rescheduled. The participant or guardian will again be given the opportunity to ask any questions before signing the consent form. The study will again be explained in detail by a study investigator and the participant or guardian will be given the opportunity to ask questions and will be reminded of their right to discontinue the study at any time. Participants or guardians will be given copies of

STUDY #: 5294

Version Date: 04/17/2023

Page 11 of 27

their written consent to participate. The original signed consent form will be stored in a locked file cabinet in the study coordinator's office for future reference.

**b)** This study includes children, a vulnerable population, and these MCC students have moderate to severe IDDs. We will administer an age/ developmentally-appropriate assent form in conjunction with guardian permission. There may be participants with IDDs that are unable to be assented due to cognitive and language limitations. We will consult MCC personnel when determining the cognitive abilities of the students. The study staff will still explain the procedures to the individual and attempt to determine their level of understanding. If determined that they cannot provide informed assent we will document this on an assent form (there is a check box on the assent forms to indicate subject's ability to provide informed assent) and proceed only with parent/guardian permission. For these participants, the staff will also use a low threshold for any indication a participant wishes to stop their participation.

c) Consent for participants with Spanish as a primary or sole or preferred language. Mary Cariola Staff whose primary and preferred language is Spanish will be consented using our Spanish Consent forms, by study personnel who speak fluent Spanish or by translators from the URMC. Two study team members are fluent in Spanish. Questionnaires have been translated into Spanish and are built into RedCap forms sent to participants based on the language used to consent them. Email contact with the link to surveys is also in Spanish. All questionnaire data on both English and Spanish forms are coded and transmitted to the data team as coded information without information about the language of the data collection form – this prevents identification of participants based on language of consent. Parents of students whose primary/preferred language is Spanish will be given the Spanish permission forms and work with one of the Spanish speaking study team members. Students at Mary Cariola are fluent English speakers and all classes are taught in English. We will use English Assent forms with students.

**d)** Alternately, the patient will be given the choice to utilize the Electronic Informed Consent (eConsent) process to provide consent remotely. This platform involves a computer based consent form accessed on personal electronic devices (e.g., computers, portable tablets, smart telephone), rather than traditional paper documentation created using a REDCap-based electronic consent form. The IRB-approved consent form will be developed in REDCap, a secure, web-based, HIPAA compliant, data collection platform with a user management system allowing project owners to grant and control varying levels of access to data collection instruments and data (e.g. read only, de-identified-only data views) for other users.

**If the patient chooses to eConsent**, a member of research team will request verbal permission to send the eConsent via email or text. The request will state: "Because URMC can't control the security of email or text messages once we send them, we need your permission to text or email you. Do you want to receive the link to the eConsent via email or text?" The permission will be documented. The email or text will not include PHI.

- The patient will be contacted by the research coordinator via telephone and/or video conference to ensure that the subject or legally authorized representative has full understanding of the study and has had ample opportunity to ask questions.
- In order to authenticate the identity of the subject or legally authorized representative signing the consent, an agreed passcode is communicated between the subject and the research coordinator. This passcode is saved as part of the subject's record for verification use later. The subject or legally authorized representative, at the

time of accessing the survey/eConsent, must then enter the passcode which is compared with the stored version entered by the research coordinator.

- Subject or legally authorized representative signatures will be obtained using a typed signature.
- Once the consent form is signed and submitted, subjects will be able to receive a print out of the paper copy, download a PDF, and/or receive an email with a PDF attachment of the signed document. The original consent form will be placed in the research record. Prospective subjects will be given the opportunity to consent to future use of information and consent to re-contact in the future.

**e)** Some students at Mary Cariola School are age 18 or older (up to 21) and have legally authorized representatives (LARs). We will use our adult consent documents and have the LAR consent to participation of the student in the study. We will also get signed assent directly from the student when they are developmentally capable of providing informed assent. There may be participants with IDDs that are unable to be assented due to cognitive and language limitations. We will consult Mary Cariola personnel when determining the cognitive abilities of the students. If determined that they cannot provide informed assent we will document this on an assent form (there is a check box on the assent forms to indicate subject's ability to provide informed assent) and proceed only with consent of the LAR. For these participants, the staff will also use a low threshold for any indication a participant wishes to stop their participation.

## 4. METHODS AND STUDY PROCEDURES

### 4.1 Study Procedures and Assessments

*Funding of study elements:* A grant to the University of Rochester from the National Institutes of Health RADx-UP program is providing funding for all aspects of the study procedures with the exception of the fingerstick blood draw and analysis of these blood samples. The fingerstick test for COVID-19 antigens is not an FDA approved test – it is solely for research purposes. Funding for this aspect of the project comes from a separate grant from the National Institutes of Health as a supplement to the University of Rochester Intellectual and Developmental Disabilities research Center.

**Questionnaire:** Staff or parents of students will be sent a unique link to a RedCap form for them to fill out. We will arrange to send this to them via email or provide them with an opportunity to fill this out on-site using a study iPad. The questionnaires are designed to collect information about the household of the subject, demographics information, attitudes and opinions regarding COVID-19 risk and testing, and vaccines. Also asked are questions about medical history, health status, drug/alcohol use.

A second link to the questionnaire will be sent all current participants to collect a cross-section of responses at a single time point – beginning mid May 2022. The questionnaires will be identical to the initial questions presented to each participant at the time of their enrollment.

#### **Asymptomatic Testing –**

**Nasal Swab:** Participating individuals (students and employees) will be tested for COVID-19 (RT-PCR) using a specimen collected using a mid-turbinete swab. This asymptomatic testing

STUDY #: 5294

Version Date: 04/17/2023

Page 13 of 27

regime starts on or after (if scheduling testing requires this to begin on a different day) enrollment and is repeated every 5-14 days for up to 36 months. Anyone testing positive is followed up as described below for symptomatic individuals.

**Saliva Sample:** For those participants (students only) that are unable to tolerate the nasal swab (mid-turbinate) test, we will use the Spectrum Solutions™ SDNA-1000 Molecular Diagnostic Saliva Collection Device. This is a self-contained, **EUA authorized** saliva collection system. It requires filling a small tube with saliva.

**Blood Samples:** Participating asymptomatic individuals (students and employees) will be tested for antibodies using the fingerstick upon scheduling first sampling visit and monthly thereafter for up to 36 months. This first blood sampling will be using a fingerstick and 1-2 drops of blood will be collected in a curette for serology testing. Possible complications include pain from the fingerstick, and a low risk of infection. The rationale for this intervention is to measure serum antibodies against SARS-CoV-2 using standard FDA approved testing methods.

A second method for blood sampling using venipuncture will be carried upon enrollment or upon scheduling the first sampling visit and subsequently, every six months for up to 36 months. In addition this method will be used for additional blood collection for MBC and DNA analyses. This second method will use venipuncture to collect ~6-10 cc of whole blood (except in students younger than 5 years in whom we will collect between 3-5cc). The possible complications of phlebotomy/venipuncture include pain, small local hematoma formation, bleeding and infection. However, this method of blood collection and testing is widely used by millions individuals daily in the United States with minimal complications, including IDD subjects. Phlebotomy will be conducted by a team specially trained in working with IDD subjects to minimize risk.

**Symptomatic Testing.** Those presenting with symptoms will be also tested for COVID-19 (RT-PCR). Those with negative test results will return to the asymptomatic testing protocol. Those with positive tests will follow NY State guidelines for quarantine/isolation. Upon return to work/school they will continue with PCR and antibody testing as described above

### **Additional Study Procedures**

The below are not accomplished using FDA approved tests and are for research use only.

**Blood Sample - Analysis of memory B cell recall responses.** [Memory B-cell \(mBC\) recall responses](#) are key to generating new antibodies against highly homologous antigenic epitopes after vaccination. [[name] and [name]](#) have demonstrated that IgG secreted by *in vitro* mBC after SARS-CoV-2 infection and vaccination contain IgG recall reactivity that includes new pathogen-specific epitope specificities. We will compare the mBC recall specificities for SARS-CoV-2 in vaccinated and unvaccinated subjects. Peripheral blood mBC in one tube (one tube – 6-10ml) of heparinized blood will be stimulated to form antibody secreting cells (ASCs) by 6 days *in vitro* culture with a combination of pokeweed mitogen, *Staphylococcus aureus* protein A, CpG ODN-2006, and IL-10. IgG secreted by ASCs *in vitro* will be analyzed by mPLEX-CoV. Antigen-specific and total IgG ASCs in the cell pellet will be enumerated by ELISpot. Antigen-specific IgG ASCs as a percentage of total IgG ASCs will quantify antigen-specific IgG mBC as a proportion of total IgG mBC .

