#### **1.4 CENTRAL AIMS**

**Scientific Goal 1: Establish a molecular testing program to monitor and identify COVID-19 infections within a school community of individuals with IDD**

**Overview and rationale:** This program will focus on the students (n=450) and staff (n=500) of the MCC, who collectively form a community that is highly representative of other IDD school communities across the nation. We will establish testing across this difficult-to-test population, using a tailored and flexible approach to foster test uptake and to prevent and/or mitigate COVID-19 outbreaks.

**Establish a clinical molecular and serological COVID-19 testing program for the Mary Cariola Center:** The dynamics of viral spread are unknown in a school serving individuals with IDD such as the MCC. Questions to be answered with *molecular* testing include: What is the incidence of asymptomatic COVID-19 infection, and how is this affected by rising vaccination rates? How do activities within the school alter risk? *Serological* testing will assess baseline prevalence of prior infection (anti-NP IgG), and changes over time, in response to infection (anti-NP IgG+) and vaccination (anti-S IgG+, anti-NP IgG-).

**Molecular Testing:** RT-PCR tests for SARS-CoV-2 with FDA EUA will deliver highly sensitive and specific clinical-grade results. Respiratory samples will be obtained by mid-turbinate or nasal swabs, collected in a dedicated area with proper ventilation and PPE (see Mobile Unit testing plan below), and delivered to the URMC Central Laboratory for testing in a CLIA environment with 24-72h turnaround times. The testing plan includes two groups: those tested as part of scheduled surveillance and those tested for symptoms or exposure.

**Surveillance Screening and Exposure/Symptomatic Testing:** Participants will be tested every 5-14 days to increase likelihood of detecting infected but asymptomatic individuals. Enrolled students and staff who report symptoms in the on-site screening will be tested on-site. Symptomatic individuals will be tested separately from asymptomatic participants every 3 days for up to 10 days. *Reported* test results will be qualitative, although Ct (cycle threshold) values will also be captured for modeling purposes.

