### Scientific Goal 2: Serological Testing and Modeling

The dynamics of the immune response to SARS-CoV-2 are as yet unknown in children with IDD, a population with prevalent immunological dysfunction, who may show different COVID-related immunological profiles and latencies to those of the general population. Here, we longitudinally follow those with IDD identified as antibody-positive, from either infection or vaccination, to quantify the timing of reductions in IgG and neutralizing antibody levels. We will use a combination of the SARS-CoV-2 clinical serological assay (described above), and a research multiplex assay for anti-spike and nucleocapsid protein IgG and receptor binding domain (RBS) antibodies, against SARS CoV-2 (including emerging virus variants), and a panel of commonly circulating human coronaviruses. *This will provide serological data uniquely focused on the IDD population with clear implications for public health immunity strategies.*

**Experimental Approach.** IgG responses to individual SARS-CoV-2 antigens (S, NP, RBD) in enrolled students and staff will be measured initially by clinical testing and fingerstick at baseline, and then every four weeks by fingerstick for up to 36 months. Any large increase in anti-SARS-CoV-2 levels will be confirmed by clinical serology. Dynamics of anti-SARS-CoV-2 IgG will be assessed by fitting the anti-S, NP and RBD quantitative results to a modified power law model that accounts for long-term antibody persistence:  $f(t) = k + \log [(1 - \lambda)(c + t)^{-\alpha} + \lambda]$ , where  $k$  is the peak log IgG level,  $\alpha$  is the decay rate,  $c$  is a constant, and  $\lambda$  is the steady-state long-term IgG level. We will fit the model using a mixed effects

**Figure 1 – Serological Testing.** (A) Clinical analysis of persistence of anti-S, anti-NP, and anti-RBD binding IgG and PCR results from the URMC Clinical Laboratory. Note the early decline of anti-NP IgG. (B) Multiplex testing for IgG directed against S proteins for common circulating coronaviruses, including SARS-CoV-2 (SARS2), and prior SARS-CoV-1 and MERS (Middle East Respiratory Virus)

method, where  $k$  and  $\alpha$  are subject specific random effects drawn from a bivariate normal distribution. This will allow comparison of decay rates ( $\alpha$ ) and steady state anti-SARS-CoV-2 IgG levels ( $\lambda$ ) across subjects.

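### The memory B-cell comparison is defined by vaccination status alone and does not account for prior infection, which the protocol names as a source of the same response

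*Protocol*

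**What the plan says.** The mBC work is described in protocol section 4.1, Additional Study Procedures, as a research-only procedure. The investigators report that "mBC after SARS-CoV-2 infection and vaccination contain IgG recall reactivity that includes new pathogen-specific epitope specificities". The next sentence gives the whole of the planned comparison: "We will compare the mBC recall specificities for SARS-CoV-2 in vaccinated and unvaccinated subjects". The ELISpot measure is then defined: "Antigen-specific IgG ASCs as a percentage of total IgG ASCs will quantify antigen-specific IgG mBC as a proportion of total IgG mBC". No stratum, restriction or covariate for prior infection follows, and the antigens are not listed there.

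The blood-draw table under Genetic Research Procedures shows a single mBC draw for adults and for minors. The SAP has no mBC endpoint, model or adjustment. It states only a general aim to study immune responses to vaccination and to infection.

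Other parts of the protocol do separate the two exposures:

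- Section 1.4, Goal 1, says that serological "testing will assess baseline prevalence of prior infection (anti-NP IgG), and changes over time". It reads anti-NP positivity as infection, and anti-S positivity without anti-NP as vaccination.
- The surveillance PCR in section 4.1 "is repeated every 5-14 days for up to 36 months".
- Goal 3 feeds serology-derived rates of prior infection and vaccination into the network models.

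None of these is tied to the mBC comparison.

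**The concern.** The comparison is meant to show what vaccination does to recall specificities. If infection also produces recall reactivity, unvaccinated subjects with a past infection carry part of the response being measured, and vaccinated subjects may carry both kinds. A two-group contrast mixes them. With one draw per subject there is no before-and-after contrast within a person to separate them.

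Prior infection cannot be presumed rare. Goal 1 describes the school as at ultra-high risk of transmission, and the adverse-event section expects that the rate of positives may be high. Follow-up runs up to 36 months, and the protocol version is dated April 2023. At stake is whether a weak, null or strong difference could be read as a vaccine effect at all.

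**Working it through.** **What can be reproduced.** Nothing. The documents give no sample size, effect, SD, alpha or power for the mBC comparison, and no prevalence of prior infection by vaccination status. The 200 staff and 50 students under Genetic Research Procedures are for DNA banking and are not the mBC sample size. Every number below is therefore an assumption, used to show how the crude contrast behaves.

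**Target.** The vaccine effect among infection-naive subjects, D.

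**Assumed inputs.** D = 0.80 SD. Infection effect I = 0.4 or 0.8 SD. Prevalence of prior infection is p_u in the unvaccinated and p_v in the vaccinated, between 0 and 0.7. SD is held at 1.

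**Formulas for the crude contrast.**

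- Additive effects: D + I(p_v − p_u).
- Non-additive effects, where a doubly exposed person has the larger of the two responses: (1 − p_v)D + p_v·max(D, I) − p_u·I. Since I does not exceed D here, this reduces to D − p_u·I.

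**Worked examples.** Additive, I = 0.8, p_u = 0.7, p_v = 0.4: 0.80 + 0.8(0.4 − 0.7) = 0.56. Additive, I = 0.8, p_u = 0.3, p_v = 0.5: 0.80 + 0.8(0.5 − 0.3) = 0.96. Non-additive, I = 0.8, p_u = 0.5: 0.80 − 0.5 × 0.8 = 0.40.

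| p_u | p_v | Additive, I = 0.4 | Additive, I = 0.8 | Non-additive, I = 0.4 | Non-additive, I = 0.8 |
|---|---|---|---|---|---|
| 0 | 0 | 0.80 | 0.80 | 0.80 | 0.80 |
| 0.3 | 0.3 | 0.80 | 0.80 | 0.68 | 0.56 |
| 0.6 | 0.6 | 0.80 | 0.80 | 0.56 | 0.32 |
| 0.5 | 0.3 | 0.72 | 0.64 | 0.60 | 0.40 |
| 0.7 | 0.4 | 0.68 | 0.56 | 0.52 | 0.24 |
| 0.3 | 0.5 | 0.88 | 0.96 | 0.68 | 0.56 |

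**What it would do to power.** Two-sided 5% test, 80% power, normal approximation: n per group = 2(1.96 + 0.84)²/d². At d = 0.80 this gives 25 per group, with power 81%. For the last column of the table:

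| Crude contrast (SD) | n per group for 80% power | Power at 25 per group |
|---|---|---|
| 0.56 | 51 | 51% |
| 0.40 | 99 | 29% |
| 0.32 | 154 | 20% |
| 0.24 | 273 | 13% |

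**Reading.** Equal prevalence with additive effects leaves the contrast unbiased. Unequal prevalence biases it either way: downward if infection is commoner in the unvaccinated, upward under additivity if it is commoner in the vaccinated. Non-additivity lowers it in these scenarios even when prevalence is equal. Restricting to, or stratifying by, correctly classified infection-naive subjects recovers 0.80 SD, but the 25 per group then counts naive subjects only.

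**The case against.** **The text is a statement of purpose, not an analysis plan.** It sits inside a laboratory procedure and gives no model, test or covariate list. A reader might infer that the investigators intend to pool infected and naive subjects, or are unaware of infection. The documents do not show that: Goal 1 and the SAP distinguish the two exposures. What stands is narrower. The only comparison written down is by vaccination alone, and nothing in either document handles infection within it.

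**The key sentence is ambiguous.** Infection and vaccination could mean combined exposure. Goals 1 and 2 treat them as separate sources of antibody, so the reading used here is the more natural one.

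**The endpoint is a set of specificities.** If the mBC panel matches the multiplex assay of Goal 1, it includes N, and N-specific recall would itself point to infection. That helps interpretation but does not remove the mixing in S or RBD recall, which can come from either source.

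**Infection history is incomplete.** It is tempting to say that it is on file for everyone. It is not:

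- Study PCR starts at or after enrolment.
- Anti-NP fades, as the Figure 1 legend in Goal 2 says: "Note the early decline of anti-NP IgG".
- Goal 1 limits the four-weekly research assay to 200 subjects, while Goal 2 and section 4.1 describe it for participants generally.
- Unvaccinated staff are tested weekly and others every 5-14 days, so ascertainment may differ by vaccination status.

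This objection limits how well the fix can work. It does not make the crude contrast sound.

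**The analysis is exploratory.** It is research-only, lies outside the five stated goals, and has no stated sample size. That is fair, and it limits how much weight the point deserves.

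**Conclusion.** The point holds as a gap in the planned comparison. The protocol names two sources of the response, contrasts subjects on only one, and draws blood once. The crude contrast is biased for the vaccine effect in infection-naive subjects if prior infection differs between the groups or if the two effects are not additive. The documents support neither equal prevalence nor additivity, but they do not rule them out.

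The size and direction cannot be computed from the documents. A reader might infer a fixed dilution: the contrast shrinks to 1 − p of the truth, that is 70%, 50% or 30% of it when 30%, 50% or 70% of the unvaccinated have been infected. That is only the special case in which infection alone gives the same response as vaccination and adds nothing in vaccinees. Neither condition is in the documents. With other assumptions the loss is smaller, nil, or becomes an inflation (0.96 against 0.80 SD). The figure is illustrative and should not be reported as an expected loss.

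The change is worth making because it is cheap, but its importance is bounded by the exploratory status of the mBC work.

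**What to change.** Add to the SAP, before the mBC data are analysed:

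1. **Main comparison.** Vaccination stratified by prior infection (vaccinated yes/no by ever infected yes/no) where cell sizes allow; otherwise a model for vaccination with prior infection as a covariate. The covariate version deals with unequal prevalence but, without an interaction term, still assumes additive effects; say so. Add time since last exposure only if dates are available. The documents do not say that vaccination dates are collected.
2. **Definition of prior infection.** Any positive PCR or any anti-NP-positive serial sample up to the mBC draw, not a single current anti-NP result.
3. **Reporting.** Name the antigens, and give S/RBD-specific and N-specific recall separately if the panel includes N. Report the number of subjects in each of the four cells.
4. **Limits.** State that infections before enrolment that have seroreverted will be classed as never infected, so some mixing will remain, and that testing frequency may differ by vaccination status.

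The cost is a short paragraph of analysis wording that uses PCR and serology the study already plans to collect; no sampling changes. The price is smaller groups. With no stated mBC sample size, some cells may be sparse or empty, and stratum results should then be presented descriptively.
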